CME	Continuing Medical Education
CFR	Code of Federal Regulations
CRF	Case Report Form
CSM	The Common-Sense Model of Self-Regulation
CTSC	Clinical and Translational Science Collaborative
DMFT	Decayed, Missing, Filled Teeth
EDC	Electronic Data Capture
EMR	Electronic Medical Record
FWA	Federal wide Assurance
GAO	U.S. Government Accountability Office
GCP	Good Clinical Practice
HHS	The U.S. Department of Health and Human Services
ICH	International Conference on Harmonisation
IPQ-RD	The Illness Perception Questionnaire – Revised for Dental
IRB	Institutional Review Board
MOC	Maintenance of Certification
MOP	Manual of Procedures
N	Number (typically refers to participants)
NIDCR	National Institute of Dental and Craniofacial Research
NIH	National Institutes of Health
OH	Oral Health
OHRP	Office for Human Research Protections
PACT	Protecting All Children's Teeth
PI	Principal Investigator
POHS	Preventive Oral Health Services
PTF	Practice-Tailored Facilitation

QA	Quality Assurance
QC	Quality Control
QI	Quality Improvement
RCC	Rainbow Care Connection
RCT	Randomized Clinical Trial
SAE	Serious Adverse Event/Serious Adverse Experience
SCT	Social Cognitive Theory
UHCMC	University Hospitals Cleveland Medical Center
UP	Unanticipated Problem
USPSTF	US Preventive Services Task Force
WCV	Well-Child Visit

PROTOCOL SUMMARY

Title: Multi-Level Interventions to Reduce Caries Disparities in Primary Care Settings

Précis: The study is a multi-site, multi-level, and multi-component cluster randomized clinical trial (RCT) to address poor dental utilization (attendance) and untreated caries among 3-6 year old Medicaid-enrolled children attending well-child visits (WCV) in primary care settings. The focus is on addressing factors (determinants) at the socio-ecological levels of the child's environment: provider (pediatrician and nurse practitioner), practice/organization level, and parent/caregiver level. Eighteen practices will be randomized to 2 arms: A) bundled multi-level intervention consisting of: 1. training medical providers in the Common-Sense Model of Self-Regulation theory-based education so that the provider delivers to the parent/caregiver the following: i) Core oral health facts about dental caries, and ii) prescription to visit the dentist and a list of dentists accepting Medicaid; 2. Integration of oral health assessments into EMR for the provider to document in the child's medical record; versus B) Control arm of medical providers receiving the American Academy of Pediatrics (AAP) based oral health education and providing usual AAP-based care for oral health. Each arm will consist of 9 practices. Children will be followed for 24 months or the completion of 3 consecutive WCV's to determine dental utilization and changes in oral health status.

[figure not shown]
Objectives:

Primary:
To examine the effectiveness of theory-based behavioral (provider level) and implementation (practice-level) bundled interventions versus enhanced usual care (AAP based oral health education) delivered by providers at WCVs in increasing dental attendance among 3-6 year old Medicaid-enrolled children.

Secondary:

- 1) Assess the effectiveness of interventions on secondary outcomes (e.g. development of new caries, changes in oral hygiene, oral health quality of life, frequency of sweet snacks and beverages, cost).
- 2) Assess potential mediators and moderators to investigate the pathways through which the multi-level interventions affect child primary and secondary outcomes.
- 3) Assess the adoption, reach, fidelity, and maintenance of providers and practices that affect child primary and secondary outcomes.

Population:	Study participants: Pediatricians/Nurse Practitioners (n = 67) and child and parent/caregiver dyads (n = 1024) will be recruited from 18 primary care practices with $\geq 20\%$ Medicaid eligible children. Practices are selected from Rainbow Care Connection (RCC), a pediatric Medicaid accountable care organization that is part of the Rainbow Research Network (Clinical and Translational Science Collaborative [CTSC] supported practice-based pediatric research network), University Hospitals Cleveland Medical Center. The recruited practices have 60 pediatricians and 7 nurse practitioners who are 73% female and 27% male. We expect child and parent/caregiver demographics to be similar to Census and Medicaid data from northeast Ohio where Medicaid-enrolled children are 61% African American, 32% Caucasian, 5% Hispanic, and 2% other.
Phase:	Phase III
Number of Sites:	18 primary care practice sites
Description of Intervention:	The bundled intervention will impact providers, the practice and the parent/caregiver. The Common-Sense Model of Self-Regulation (CSM)-based education and skills training for the pediatrician or nurse practitioner are designed to educate them regarding chronicity of caries and teach them how to communicate core oral health facts to the parent/caregiver, provide a prescription to take the child to the dentist together with a list of area dentists who accept Medicaid, and document oral health in the EMR. The parent/caregiver will receive the CSM-based facts from the providers and should take their child to the dentist and improve oral health behaviors in the home. The practice level intervention will be enhancements to the EMR system to include oral health status for quality improvement of records and to use for follow-up with the parent/caregiver at subsequent wellchild visits.
Study Duration:	Approximately 36 months
Subject Participation Duration:	Parent/Caregiver = 24 months or completion of 3 WCV's Providers = 24 months or completion of 3 consecutive WCV's of enrolled patients. Additionally, all providers will complete a follow-up structured interview and debriefing session.
Estimated Time to Complete Enrollment:	9 months
Schematic of Study Design:	

2 INTRODUCTION: BACKGROUND INFORMATION AND SCIENTIFIC RATIONALE

2.1 Background Information

Dental caries (tooth decay) is the leading chronic childhood disease (HHS, 2000). Its prevalence in the primary dentition among 2-8 year old children increased from 35% (1988-1994) to 37% (2011- 2012) and failed to meet Healthy People objectives (Dye et al., 2009). Although caries experience and untreated caries among 2-8 year old children have decreased nationally, poor and minority children still have a higher burden of disease compared to their affluent counterparts (Dye et al., 2017). In Cleveland, our community-wide study indicated an untreated primary caries rate of 42% ([name] et al., 2012), much higher than the national average of 14% (Dye et al., 2015). Medicaid claims data from 2007 and 2008 indicates that median dental utilization among Medicaid-enrolled children was only 33-37% (Hakim et al., 2012; United States General Accounting Office, 2008). Recent self-reported surveys indicate that 50.6% of Medicaid-enrolled children compared to 69.0% of non-Medicaid enrolled children visited the dentist in the last six months (Yarbrough et al., 2014). For 13% of Medicaid-enrolled young children, their first dental visit was for emergency care (Divaris et al., 2014). There is clearly a dental care gap among 3-5 year-old Medicaid-enrolled children with 39% having had a dental visit (Hakim et al., 2012), despite anticipatory guidance for preventive dental visits starting from age 1 (AAPD, 2014), while 67% (3-6 year olds) received a well-child visit (USPHS, 2015).

Due to the disparate burden of caries among young children (Dye et al., 2010), primary care pediatric settings have been recommended to provide preventive oral care including referral to a dentist. But, a recent systematic review by the U.S. Preventive Services Task Force (USPSTF) to update its recommendation for medical primary care clinicians concluded that there is lack of evidence on effectiveness of parent/caregiver educational interventions and primary care referral to dentists (Chou et al., 2014).

The few retrospective cohort studies that have examined the effectiveness of non-dental primary care providers delivering preventive oral health services (POHS: such as screening exams, dentist referral, fluoride varnish) to young Medicaid-enrolled children have resulted in lower decayed missing filled teeth (dmft) in kindergarteners who received POHS compared to those who did not (Kranz et al., 2015). The number of dmft at age 5 was similar regardless of the type of provider (primary care vs. dentist) delivering POHS (Kranz, Rozier et al., 2014). Distance from physician-based POHS did not impact the likelihood of the child having a medical visit, while distance from a dental practice lowered dental utilization (Kranz, Lee et al., 2014). One recent study found that caries-related expenditures (using Medicaid claims data from Alabama) among children <6 years were significantly higher for those receiving dentistdelivered early preventive care versus those not receiving early care, while there was no difference between receiving early preventive care from a primary care provider versus not (Blackburn et al., 2017). But, Milgrom and Cunha-Cruz (2017) in a letter to the editor regarding Blackburn et al.'s study, point out that there are several methodological limitations and that the efficacy of fluoride varnish is dependent on being delivered according to a periodic schedule that can be affected by missed well-child visits which may have impacted their study conclusions. Thus, our proposed randomized clinical trial has the potential to address the limitations of prior retrospective studies in terms of testing behavioral interventions in pragmatic settings with

careful control for confounders and longitudinal follow-up of children with clinical and claims data. The interventions being tested also offer the opportunity to lower untreated decay and increase dental utilization in 3-6 year-old Medicaid-enrolled children, two outcomes which were not able to be achieved in prior retrospective studies (Kranz, Rozier, et al., 2014; Kranz, Lee, et al., 2014; Kranz et al., 2015). Additionally, in dental settings the effectiveness of interventions with oral health (OH) education or motivational interviewing have been inconclusive and these interventions have had limited success in eliminating or reducing caries disparities in young children (Beauchamp et al., 2008; Casamassimo et al., 2014; Griffin et al., 2008; Kay & Locker, 1996; Lee & Divaris, 2014; P. Milgrom et al., 2009; Sgan-Cohen et al., 2013).

The literature is clear that most low-income parent/caregivers see dental diseases as acute to be responded to only when there is pain or visible decay (Hooley et al., 2012). One approach shown to be useful in changing this reasoning process and for self-management of chronic medical conditions is the Common-Sense Model of Self-Regulation (CSM) (Leventhal et al., 1997; Leventhal et al., 2003). The CSM is a psychological approach where individuals create a mental representation (or perception) of their illness based on the abstract and concrete sources of information available to them. Six key domains guide the cognitive illness representation: identity, cause, consequence, timeline, cure or controllability, and illness coherence. The CSM being a “parallel-processing” model requires an emotional domain since individuals use past illness experience, cognitive, and emotional representation to self-manage their illness (Moss-Morris et al., 2002). In this manner the CSM is unique from other social cognitive and health behavior theories (Edgar & Skinner, 2003). A negative or positive illness perception is formed from three sources of information (Hagger & Orbell, 2003): cultural knowledge of illness; information from external environment such as doctor/dentist or parent; and illness threat from past and current experiences with the disease. Based on the CSM, the revised illness perception questionnaire (IPQ-R) was developed (Moss-Morris et al., 2002) and adapted for various chronic illnesses with good reliability and validity (Abubakari et al., 2012; Brink et al., 2011; Cabassa et al., 2008; Chen et al., 2008; Hurt et al., 2010; Lobban et al., 2005). Illness perception has been demonstrated empirically in other medical and psychological illnesses to predict health outcomes (Covic et al., 2004; Fowler & Baas, 2006; Giannousi et al., 2010; Hou et al., 2010), and in development of behavioral interventions to change perception and improve health outcomes (Davies et al., 2008; Galli et al., 2010; Mosleh et al., 2014). Recently, our research team has shown that caregivers who believed baby teeth do not matter had significantly less accurate illness perception of dental caries compared to caregivers who believed baby teeth do matter utilizing the illness perception questionnaire revised for dental (IPQ-RD) that the team developed and validated ([name] et al., 2017). So, CSM-based behavioral interventions have the potential to modify caregiver caries perception, and improve dental utilization for young children.

This multi-site, multi-level, and multi-component cluster randomized clinical trial (RCT) will assess dental utilization among children following oral health interventions in the primary care setting. The intervention mapping framework was used to develop the theory-based multi-level interventions at the provider and practice level (Bartholomew & Mullen, 2011). Drawing on emerging concepts from the medical literature, the common-sense model of self-regulation (CSM) was used as the underlying theory for the provider-level interventions. Traditionally, oral health education has provided disjointed factual knowledge at the parent/caregiver level. In this

study, providers are first trained in the organized CSM-based education to understand the chronicity of caries, and then taught to use the CSM framework to deliver key oral health facts to parent/caregivers with the goal of improving their cognitive and emotional representation with a chain of reasoning of the caries process. Other supporting theories such as the Social Cognitive Theory (SCT) are also used to improve the skills and self-efficacy at the provider level to communicate the oral health facts (Bandura, 1991). Providers will develop skills in 5 areas: 1) introduce the topic of dental care in routine clinical encounters, 2) strategies to effectively provide brief advice, 3) strategies to elicit and address parent/caregiver concerns in a nonconfrontational manner, 4) provide a prescription for the child to go to the dentist and a list of area Medicaid-accepting dentists, and 5) document oral health encounter in EMR. At a practice level, integration of OH documentation in EMR may be influenced by practice attributes and champion/s in accordance with Roger's diffusion of innovation theory (Greenhalgh et al., 2005; Rogers, 2003).

While the focus is on addressing factors at three levels of the child's environment (practice, provider, parent/caregiver, the multilevel experimental study interventions are at the provider (behavioral) and practice (implementation) levels. The parent/caregiver will be the recipients of the provider- and practice- level study interventions.

Provider (Pediatrician or Nurse Practitioner): (1) Providers will receive theory-based training to improve knowledge and skills using CSM and SCT frameworks; (2) Providers will communicate to parent/caregiver the CSM-based oral health facts, and provide prescription to go to the dentist + a list of Medicaid accepting dentists.

Parent/caregiver: Parents/caregivers will receive from the provider, CSM-based oral health facts and a prescription + list of Medicaid- accepting dentists to increase the child's dental attendance and improve oral health of the child, including oral hygiene behaviors in the home.

Practice (Pediatric): Practices will integrate documentation of oral health status in the EMR for quality improvement and to inform the providers of the child's oral health status and previous CSM-based oral health facts (maintenance of the intervention) .

2.2 Rationale

Ten million U.S. preschool and school-age children have untreated caries and profound disparities exist by race, socioeconomic status, and geographic region. Our studies in Cleveland have found that school dental screenings have not been effective in stimulating dental attendance ([name] et al., 2012) despite eligibility under the Affordable Care Act and coverage through Medicaid. Our pilot study results among 86 three to six year old Medicaid-enrolled children indicate that 36% (31 out of 86) had untreated dental caries (cavitation), much higher than the national average of 18% (Dye et al. 2017).

There are three core parent (or caregiver) issues: (1) awareness of importance of caries-free primary teeth; (2) understanding dental caries as a chronic disease that can be present even without symptomatic tooth pain; (3) navigating resources for dental care access. Thus, an accurate perception of dental caries is required for parental self-management strategies to take

care of their child's oral health needs. Also important is that parent/caregivers receive consistent OH facts from primary care settings, where young children are most often seen. In one study, two to five year old children were 3 times more likely to visit a dentist when advised by a primary health care provider, but this study also reported that low-income families were less likely to be advised (Beil & Rozier, 2010).

Interventions that improve dental attendance among disparate populations are likely to reduce caries disparities. In this study, parents/caregivers are recipients of the intervention through a dissemination channel from providers to parents/caregivers. Parents/caregivers are not the direct target of the intervention, but indirectly benefit through the provider. This active dissemination strategy builds on evidence that parents/caregivers perceive healthcare providers to be trusted resources for health information (Nyhan et al. 2014). By enhancing dental knowledge and skills of the pediatric providers through the CSM-based education, interactive practice sessions with standardized patients, and training in EMR documentation, we hypothesize parents/caregivers will receive this new information along with coping and action supports (e.g., prescription to the dentist, list of Medicaid accepting dental providers) from the child's provider. As a result, we hypothesize that providers with improved knowledge regarding the chronicity of caries and appropriate skills training will deliver consistent reinforcing oral health facts to parents (at annual WCVs) that will result in increased dental utilization for their child compared to those providers delivering usual care based on AAP education.

There are three pathways to dissemination of evidence-based interventions: The first pathway which is the most common is the "direct to practice" through the development of an exportable package or toolkit distributed through professional or public-health organizations; The second pathway involves "policy to practice" through establishment of policies to be followed by organizations or communities; The third pathway is systematic "diffusion research" to assess the effectiveness of different dissemination methods, and one that is least frequently used. A qualitative study among primary care providers indicated that health professionals require a tool kit that is demonstrated to be effective, easy to tailor and apply, has a table of contents to navigate to the relevant content, infrastructure/organizational support, and availability of support from practice facilitators or other experts. Further, tool kits can be an effective knowledge transfer strategy. Few theory-based tool kits exist for oral health interventions in primary care, therefore to address this gap we will develop a tool kit according to the first pathway utilizing the evidence from our cluster randomized clinical trial and the qualitative findings.

2.3 Potential Risks and Benefits

2.3.1 Potential Risks

Children: Children may experience some discomfort during the screening exam from keeping their mouths open for up to two minutes. There is also a chance that confidential information can be lost but we will use every precaution to protect the information we collect.

Parents/Caregivers: Some people are uncomfortable answering questions about themselves for research. We will try to make participants feel as comfortable as possible. There is also a chance that confidential information can be lost but we will use every precaution to protect the

information. The oral health portion will add increased time to the well child visit that may impact parent/caregiver schedule and parking fees (if required to pay for parking).

Providers: Some people may feel uncomfortable being audiotaped or observed by study staff. We will try to make providers feel as comfortable as possible. There is also a chance that confidential information can be lost but we will use every precaution to protect the information we collect. As a result of participating in this study, there would be additional time added to the well-child visit that can potentially lead to some loss of productivity for providers.

2.3.2 Potential Benefits

Child participants may benefit by learning how to take care of his/her teeth and/or from their parent/caregiver learning about oral health. Parents/caregivers will receive information about taking the child to the dentist for preventive visits.

Providers may benefit from participating in the study by learning about oral health facts, integrating an oral health protocol into practice routines, and best practices for communicating oral health facts to parents/caregivers. EMR Documentation of oral health will help the providers to follow-up with the parent at the next well-child visit and be useful for practice quality improvement.

3 OBJECTIVES

3.1 Study Objectives

Primary Objectives:

- 1) To examine the effectiveness of theory-based behavioral (provider-level) and implementation (practice-level) bundled interventions versus enhanced usual care (based on AAP oral health education) delivered by providers at WCVs in increasing dental attendance among 3-6 year old Medicaid-enrolled children.

Secondary Objectives:

- 1) Assess the effectiveness of interventions on secondary outcomes (e.g. development of new caries, changes in oral hygiene, oral health quality of life, frequency of sweet snacks and beverages, cost).
- 2) Assess potential mediators and moderators to investigate the pathways through which the multi-level interventions affect child primary and secondary outcomes.
- 3) Assess the adoption, reach, fidelity, and maintenance of providers and practices that affect child primary and secondary outcomes.

3.2 Study Outcome Measures

Primary and secondary effectiveness outcomes will be assessed at the child level.

3.2.1 Primary Outcome Measures

The primary outcome will be dental attendance (receipt of dental care as yes/no, and number of visits). The primary outcome will be determined through a hierarchical process where Medicaid dental claims data (Current Dental Terminology (CDT) codes for preventive or restorative procedures in the past 12 months) would be the primary measure, followed by assessments through clinical dental screenings (restoration or extraction between WCVs #1 and #2, and between WCVs #2 and #3), conducted by calibrated examiners (See Section 14.2).

3.2.2 Secondary Outcome Measures

Secondary outcomes will be assessed through clinical dental screenings for new primary and permanent decayed and filled teeth (dft/DFT: number of new cavitated lesions or restorations on teeth that were previously sound and number of new restorations on teeth that were previously decayed at the baseline WCV), questionnaire responses for oral hygiene (frequency of tooth brushing), diet (frequency of sweet food and drinks), and oral health-related quality of life (ECOHIS, numeric score) (Pahel et al., 2007). The direct and indirect dental costs will be assessed through various sources (See Table 8.1.2 for more details on cost elements and sources).

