4 STUDY DESIGN

This study will utilize a multi-site, multi-level, and multi-component cluster randomized clinical trial design (Phase III) to assess interventions intended to address poor dental utilization (attendance) and untreated caries among 3-6 year old Medicaid-enrolled children attending well-child visits (WCV) in primary care settings. The focus is on addressing factors (determinants) at the socio-ecological levels of the child's environment: provider (pediatrician and nurse practitioner), parent/caregiver and practice/organization levels. Eighteen practices will be randomized to 2 arms for provider training and practice/organization level study intervention changes: A) provider-level CSM training, provision of oral health facts to parents, a prescription and a list of dentists accepting Medicaid + practice-level EMR changes for documenting oral health; B) AAP training with no prescription or list of dentists accepting Medicaid and no changes to the EMR. Arm A parents/caregivers will receive oral health facts and prescription to take their child to the dentist and improve oral health behaviors in the home, while Arm B parent/caregivers will receive usual AAP-based care for oral health. Each arm will consist of 9 practices (n= 18), 33 to 34 providers (n= 67), and 512 parent/caregiver and child dyads (n= 1024). Each parent/caregiver and child dyads will be recruited at the first WCV and then followed for two consecutive WCVs (for a 24 month duration or until the subject has completed 3 well child visits). Each provider will complete the didactic and skills training prior to enrolling any parent/caregiver and will participate in the study for a total of 24 months duration (includes initial and booster didactic and skills training: 3 months, WCV#1: 3 months, WCV#2: 3 months, WCV#3: 3 months). Data will be collected prior to WCVs, at WCVs, and follow-up visits.

Immediately after randomization of practices, recruitment will be rolled-out, i.e. parent/caregivers will be recruited during a 3-month period in 6 practices at a time, with recruitment at all 18 practices expected to be completed in 9 months. This strategy will maximize staff time and ensure that EMR integration of OH is complete at practices randomized to Arm A, and that providers receive the didactic and skills training prior to their practice's rollout.

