- A newly carious tooth is defined as any tooth receiving an ICDAS lesion code ≥ 3 that received a sound code on the previous dental screening or any tooth surface with an ICDAS filling code ≥ 3 that previously did not have one. Number of teeth with new decay or filling will be assessed through the clinical dental screenings (T_0 , T_3 , and T_6) and recorded on the ICDAS Assessment form (Appendix E).
- Questions on frequency of tooth brushing (NHANES III)(CDC), frequency of consumption of sweet food and drinks (NHANES 2009-2010; Youth Risk Behavior Survey 2017)(CDC, 2017; CDC, 2014), and the 13-item Early Childhood Oral Health Impact Scale (ECOHIS)(Pahel et al., 2007) will be used to measure oral hygiene, frequency of sweet food and drinks, and oral health-related quality of life (OHRQoL), respectively. Higher scores on

the ECOHIS indicate poorer OHRQoL. These questions are included on the A2: Parent Questionnaire (Appendix E) which will be completed at all 3 WCVs (T_0 , T_3 , and T_6).

- Direct dental costs include costs of preventive and restorative procedures, and dentalrelated ED visits. These costs will be abstracted from Medicaid claims files as part of the verification of child's dental care receipt (described above) and recorded on the Medicaid Claims Abstraction form. Non-dental direct costs (transportation) and dental indirect costs (time away from work, household, or leisure activities) are measured using questions adapted from the Annotated Cost Questionnaire (Thompson & Wordsworth, 2001) which are incorporated into the B2 Follow-up Questionnaire. The B2 Questionnaire will be administered after WCVs #1 and #2 (T_1 and T_4). Study staff will administer the cost questionnaire at WCV #3 (T_6) to identify any lags in receipt of dental care. Cost data from Medicaid claims files will be abstracted at 3 time points (T_1 , T_4 , and T_7). See the Annotated Cost Questionnaire and Medicaid Claims Abstraction form (Appendix E) for more details.

Table 8.1.2 Cost elements and sources

Cost Category	Cost Element	Source
Implementation/ training costs	Training providers in communicating oral health facts	Study training records/logs
	IT system modifications	Vendor invoices, clinic personnel time logs
	Staff training	Study staff time/training logs
Intervention costs	Time required to provide education and give prescription	Review of audiotaped encounters
	Cost of dental prescription pads, flip charts, pocket cards	Study/practice expense records

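### Untreated decay is a stated target of the trial but not a defined secondary outcome, and the planned dft count rises when existing decay is treated

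*Combined protocol and SAP*

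**What the plan says.** **Stated purpose.** The Protocol Summary says the trial is "to address poor dental utilization (attendance) and untreated caries among 3-6 year old Medicaid-enrolled children", and section 4 describes its design as one "to assess interventions intended to address poor dental utilization (attendance) and untreated caries". Section 2.1 says the interventions may "lower untreated decay and increase dental utilization in 3-6 year-old Medicaid-enrolled children, two outcomes which were not able to be achieved" in earlier retrospective work. Section 2.2 cites untreated cavitation in 31 of 86 pilot children.

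**Defined outcomes.** Section 3.1 gives, as examples of secondary outcomes, "development of new caries, changes in oral hygiene, oral health quality of life, frequency of sweet snacks and beverages, cost". Section 3.2.2 defines the caries outcome as "new primary and permanent decayed and filled teeth (dft/DFT: number of new cavitated lesions or restorations on teeth that were previously sound", together with the "number of new restorations on teeth that were previously decayed at the baseline WCV". Section 8.1.1 pools the same two things: "Number of teeth with new decay or filling will be assessed through the clinical dental screenings". Table 8.1.1 scores new caries as decayed and filled teeth. None of these places lists untreated decay.

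**Analysis.** Section 12.2 hypothesises a lower mean dft in Arm A. Section 12.4 names dt/dft as an example of a proportion outcome, modelled by GEE with a logit link and a beta-binomial or zero-inflated beta-binomial distribution. It does not say at which visit dt/dft is taken, whether it uses new or prevalent teeth, or what happens when dft is zero.

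**The concern.** If the intervention brings more children to a dentist, one direct clinical consequence is that lesions already present get treated. The defined caries outcome does not reward this. A restoration on a tooth that was decayed at baseline goes into the count as a new event, while the same tooth left decayed contributes nothing. On that component, an arm that treats more existing disease scores worse on an outcome expected to improve.

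A report could then show higher attendance beside flat or slightly higher dft, and readers might conclude that the visits brought no oral-health gain. The quantity that would settle the matter, how many children still have untreated decay at the end, has no prespecified definition or analysis. Any version produced after the arms are compared would be open to the charge of selection.

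**Working it through.** **1. The plan's own dft power.** Inputs from section 12.2: 512 per arm, 25% dropout, 9 practices per arm, ICC 0.02, means 4.5 and 2.7, SD 7, two-sided 0.05.

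- Analysed per arm: 512 × 0.75 = 384. Per practice: 384 / 9 = 42.67.
- Design effect: 1 + 41.67 × 0.02 = 1.833. Effective n: 384 / 1.833 = 209.5 per arm.
- Standard error of the difference: 7 × √(2 / 209.5) = 0.684. Power: Φ(1.8 / 0.684 − 1.96) = 0.749, or 0.747 by noncentral t.

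The stated 74% is reproduced. It applies to the pooled count only; no power is given for untreated decay or dt/dft.

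**2. What one tooth contributes (section 3.2.2).**

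| Baseline | Follow-up | Adds to new dft | Untreated at follow-up |
|---|---|---|---|
| Sound | Cavitated | 1 | Yes |
| Sound | Restored | 1 | No |
| Decayed | Still decayed | 0 | Yes |
| Decayed | Restored | 1 | No |

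The first two rows cannot be told apart by the count. The last two run opposite to benefit.

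**3. How large the adverse component could be.** The documents do not give the number of decayed teeth per affected child; call it t, an assumption. Take 36% of children with decay at baseline, and suppose that the planned 0.16 attendance difference (0.46 − 0.30) applies to them and that every extra attender has all t teeth restored. Mean new dft in Arm A then rises by 0.36 × 0.16 × t = 0.058t, which is 0.06 tooth at t = 1 and 0.29 at t = 5. This compares with a hypothesised fall of 1.8 and a standard error of 0.68. The direction follows from the definition. The size is small if prevention works as hoped, and matters if the preventive effect is small.

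**4. Why dt/dft does not fill the gap.** A child with 2 decayed and no filled teeth has 2/2 = 1. A child with 2 decayed and 2 filled teeth has 2/4 = 0.5. The share halves with the same number of untreated teeth. It has no value when dft = 0, so caries-free children drop out. If follow-up dft is the denominator, the children analysed are selected after randomisation.

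**5. Illustrative power for untreated decay (yes/no) at WCV #3.** Same 384 per arm and a pooled two-proportion z test, as section 12.2 uses for attendance. Check on the primary outcome: ICC 0.04 gives effective n 144.0, and 0.46 against 0.30 gives power 0.802 (stated 80%). The documents give no control rate at WCV #3, so three are assumed: 36% (the pilot rate), 42% (the community rate cited in section 2.1) and 25% (a lower bound for illustration). Entries are the Arm A rate detectable with 80% power.

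| Assumed control rate | ICC 0.01 (effective n 271.1) | ICC 0.02 (209.5) | ICC 0.04 (144.0) |
|---|---|---|---|
| 25% | 15.4% | 14.2% | 12.2% |
| 36% | 24.9% | 23.5% | 21.1% |
| 42% | 30.5% | 28.9% | 26.4% |

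These ignore the small-cluster correction planned in section 12.4, which lowers power. For scale, referring the dft test to a t distribution with 16 degrees of freedom (18 practices less 2) takes its power from 0.747 to 0.695. They also ignore any gain from adjusting for T0 status.

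**The case against.** The strongest reply is that the plan does deal with untreated decay. Section 12.4 names dt/dft and gives it a model, and dt/dft does separate decayed from filled teeth. Treatment of known lesions is recorded too: section 8.1.1 counts restoration or extraction of a tooth with a prior active lesion as evidence of attendance, and restorative procedure codes are abstracted from claims. The primary objective and the hypothesis in section 12.1 concern attendance only, and the secondary list in section 3.1 is explicitly one of examples.

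Much of this stands, and it rules out several stronger readings that a reader might infer:

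- That untreated decay is absent from the plan, or that the trial cannot show a change in it. The dt/dft example and the ICDAS lesion and filling codes recorded at all three visits contradict this.
- That treatment of existing lesions goes undetected. It is captured as evidence of attendance and within dft itself.
- That half the trial's purpose goes unanswered. Untreated caries is part of the problem addressed; the primary question is attendance.
- That dft will show harm. Step 3 of the working gives a wrong-direction component whose size depends on assumptions and may be small.

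What the reply does not supply is a defined comparison of remaining untreated decay in all screened children. Restoration of a known lesion as a marker of attendance, second in rank to claims, is not that comparison. Nor is an example ratio with no visit or denominator.

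**Conclusion.** The point holds as an inconsistency between the stated target and the defined outcomes, together with a dft definition that scores treatment of baseline decay in the unfavourable direction. It does not touch the primary analysis. About 369 of 1,024 children (31/86 × 1,024) would enter with untreated cavitation if the pilot prevalence carries over, so the group in which the problem arises is not small.

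The direction of the dft problem rests on section 3.2.2 alone. Its size rests on assumptions about how many teeth are restored. The power figures are illustrative: the pilot's 36% is a rate in children aged 3 to 6, not a WCV #3 control rate, and the ICCs are borrowed from other outcomes. The detectable falls, 11 to 15 percentage points at a 36% control rate, are large but of the same order as the 16 points assumed for attendance. An estimate with its confidence interval would be informative even where the test is not.

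**What to change.** Reconcile sections 3.2.2, 8.1.1 (with Table 8.1.1) and 12.4 before the arms are compared:

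1. Add a secondary outcome: untreated decay at WCV #3 in all screened children, meaning any primary or permanent tooth with an unrestored ICDAS lesion code ≥ 3 (yes/no), with the number of such teeth as support. Analyse it with the GEE and small-cluster correction already planned, adjusted for untreated decay at T0. State how naturally exfoliated teeth are handled, consistently with the age rule in section 8.1.1, so that a carious primary tooth lost naturally is not read as decay resolved.
2. Report new caries on previously sound teeth separately from new restorations on teeth decayed at baseline, and say which of the two the hypothesis of a lower dft concerns.
3. Replace dt/dft, or keep it as supportive with its visit, tooth set and treatment of dft = 0 stated.

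The cost is wording in the protocol and analysis plan and one more secondary outcome to report. No new data are needed.
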